**Table 1-4: Schedule of Activities for Part A (monotherapy dose escalation)**

Assessments	Screening a		Treatment a										SFU Visit a	Final Visit a		
	-28 to -1	-14 to -1	Cycle 1 (28 days)				Cycle 2 (28 days)				Cycle 3 onwards c (28 days)					
Cycle day			1 d	2/3	8	15 d /16	22	1 d	8	15 d	22 e	1 d	15 d	22	Within 30 days after last dose f	3 months after last dose f
Blood collection for transcriptomic analysis n			X			X z		X				X			X	
Blood collection for genetic analysis			X													
Blood collection for ctDNA analysis			X			X z		X				X aa			X	
Echocardiogram		X						X				X bb			X	
Tumor assessments cc	X t									X u			X v	X cc		
Tumor biopsy for PD analysis w	X					X										
Historical tumor sample (from prior to entry into study) if available x	X															
Concomitant medication	X	X	Recorded throughout										X			
Adverse events (including DLT in Cycle 1)	X	X	Recorded throughout										X y			
Survival census ff													X	X		

AE=adverse event; ALP=alkaline phosphatase; ALT=alanine transaminase; ANC=absolute neutrophil count; AST=aspartate transaminase; COVID-19=SARS-CoV2 (COVID-19) pandemic; CR=complete response; CT=computed tomography; ctDNA=circulating tumor DNA; ECG=electrocardiogram; ECOG=Eastern Cooperative Oncology Group; h=hours; hCG=human chorionic gonadotropin; iv=intravenous; LDH=lactate dehydrogenase; MRI=magnetic resonance imaging; PD=pharmacodynamic(s); PK=pharmacokinetic(s); PR=partial response; PSA=prostate specific antigen; RBC=red blood cell; SFU=Safety Follow-Up; SMC=Safety Monitoring Committee; WBC=white blood cell

a Allowed visit window:  $\pm$  2 days (unless specified otherwise). Note: Day 2 of Cycle 1 must occur on the scheduled day relative to Day 1, due to the PK sampling. See PK schedule for allowed sample windows for PK. If needed in context of the COVID-19 pandemic, assessments currently scheduled for Day -28 to Day-1 and assessments scheduled for Screening Days -14 to -1 may be combined into 1 visit conducted within 14 days of first dose.

b Deleted.

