c From Cycle 3 and Cycle 4 onwards, visits on Day 22 may be omitted at the discretion of the investigator and based on toxicity seen at Cycle 1 and 2, unless these visits were required for tumor assessments, or participant assessment.

d The following safety assessments will be performed predose: physical examination, vital signs, hematology, blood chemistry, coagulation, urinalysis, pregnancy testing, ECOG performance status, echocardiograms, and ECG. All other safety assessments will be performed postdose.

e The visit on Day 22 may take place at any point from Day 21 to Day 28 of Cycle 2; tumor assessments should take place within this window at the investigator's discretion.

f When participants are unable to attend the SFU or Final Visit, it will not be considered a protocol deviation.

g Informed consent must be given before any study-specific Screening procedures are performed.

h ECGs are to be performed in triplicate with the participant in a supine position after a minimum of 5 min rest. When ECG coincides with PK (and PD), the ECG should be performed first. On Days 1 and 15 of Cycle 1, triplicate ECGs should be performed 3 times: the first predose; the second at the end of the infusion; and the third 8 hours after the end of the infusion. For all other cycles, triplicate ECGs should be performed predose.

i Pregnancy tests measure serum or urine  $\beta$ -hCG. Serum tests should be performed at Screening and visit immediately before the investigational product administration on Day 1 Cycle 1. Serum or urine pregnancy tests must be performed prior to dosing on dosing days. Additional pregnancy tests should also be performed during the study if indicated.

[figure not shown]
j UCB6114 is administered as an iv infusion on Days 1 and 15 of each cycle, until the occurrence of progressive disease, unacceptable toxicity, or withdrawal of consent.

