t Screening tumor assessments including contrast-enhanced spiral CT or MRI scan of the chest, abdomen, pelvis, and any other areas of known or suspected disease, must be obtained within 42 days prior to starting study medication. If there is a contraindication to iodinated iv contrast, chest CT should be performed without iv contrast and MRI scans (with gadolinium chelate contrasts) of the abdomen and pelvis may be used instead of CT scans of the abdomen and pelvis. A CT or MRI scan that is dated prior to consent (up to 42 days prior to starting study medication) for this study may be used as the Screening assessment, where this has been performed as per standard care or at the end of a prior research study. The same method of assessment is to be used per participant for the duration of study participation.

u Further tumor assessments are to be performed between Days 21 and 28 of every even cycle ( $\pm 2$  days).

v Tumor assessments are to be completed on even cycles.

w If there are accessible tumor lesions, optional biopsies may be performed at Screening and at Cycle 1 Day 22. The allowed time-window for collection of the Cycle 1 Day 22 sample is from Cycle 1 Day 22 up to Cycle 2 Day 22.

x If an historical tumor biopsy specimen obtained prior to the participant's entry into the study (eg, at the time of diagnosis) is available, samples of this tissue will be requested for PD analysis.

y Follow-up of AEs: AEs will be recorded up to 30 days after the last dose of study medication. After that time, any unresolved drug-related AEs should be followed until resolution or stabilization of the AE to obtain the date of resolution/stabilization (this follow-up can be via routine clinic visits or correspondence with a treating physician or other healthcare professional).

z Assessed on Day 15 only of Cycle 1.

aa Only at Day 1 of Cycle 3.

bb Echocardiograms are to be completed on even cycles from Cycle 3 onwards.

cc Tumor assessment at SFU is not required if the participant has withdrawn due to progressive disease or if the previous tumor assessment was within 42 days of SFU visit.

dd At visits where UCB6114 is administered, circulating gremlin-1 samples will be collected predose as described in Section 8.8.1.

ee Cycle 1 Day 1, the eligibility assessment will be performed predose.

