**Table 1-7: Schedule of Activities for Part B**

Procedure	Screening		Treatment					SFU Visit	Final Visit	
	-28 to -1	-3 to -1	Cycle 1 & Cycle 2 (28 days)			Cycle 3 onwards (28 days)				
Cycle day			1	8	15	22	1	15	Within 30 days after final dose	3 months after final dose
Informed consent a	X									
Eligibility assessment b	X	X	X g							
Demographic data and height	X									
Medical/surgical/cancer history/concomitant disease and current medical status	X		X g							
ECG c	X	X	X		X		X		X	
Pregnancy test, if applicable d	X	X	X				X		X	X
TFD/TPI dispensing e		X	X							
TFD/TPI administration			TFD/TPI is administered orally twice daily on Days 1 to 5 and Days 8 to 12 of each cycle							
UCB6114 administration			UCB6114 is administered as an iv infusion on Days 1 and 15 of each cycle							
Physical examination and weight f	X	X	X	X g	X	X g	X	X		X
Vital signs (BP, HR, RR, and temperature) h	X	X	X	X g	X	X g	X	X		X
ECOG performance status h	X	X	X	X g	X	X g	X	X		X
Urinalysis i	X	X	X		X	X	X			X
Urinalysis for urinary markers of bone turnover			X		X		X			X
Hematology k	X	X	X	X	X	X	X	X		X
Blood chemistry l	X	X	X	X	X	X	X	X		X
Coagulation m	X	X	X		X g		X			X

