**Table 3-1: Objectives and endpoints for the dose escalation module (Part A) and the dose optimization module (Part A1)**

Objectives	Endpoints
Primary	
To characterize the safety profile of UCB6114 as monotherapy	Incidence of TEAEs Severity of TEAEs Incidence of DLTs
Secondary	
To characterize the PK of UCB6114 administered as monotherapy	UCB6114 concentration by scheduled assessment and cohort
Tertiary/exploratory	
To document any antitumor activity observed with UCB6114 according to relevant RECIST criteria	Antitumor activity as indicated by: 

• ORR

• DCR

• DOR

• PFS

• OS

To explore PD biomarkers of UCB6114	

• Change in transcriptional and protein marker levels in blood and tumor tissue by scheduled assessment and cohort

• Change in ctDNA levels in blood by scheduled assessment and cohort

To evaluate the incidence, emergence, and impact of ADA	ADA (anti-UCB6114 antibody) titer and sample status by scheduled assessment

ADA=antidrug antibody; ctDNA= circulating tumor DNA; DCR=disease control rate; DOR=duration of antitumor response; DLT=dose-limiting toxicity; ORR=objective response rate; OS=overall survival; PD=pharmacodynamic(s); PFS=progression-free survival; PK=pharmacokinetic(s); RECIST=Response Evaluation Criteria in Solid Tumors; TEAE=treatment-emergent adverse event

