## 10.3 Planned safety and other analyses

### 10.3.1 Safety analyses

Safety will be assessed by clinical review of all relevant parameters including AEs, SAEs, laboratory values, vital signs, echocardiograms, ECG results and physical examination. Eastern Cooperative Oncology Group performance status will also be assessed from a safety perspective. Unless specified otherwise, the safety analyses will be conducted for the SS defined in Section 10.1. The results of these analyses will be presented by study part. For the dose escalation modules of the study (Part A, B, and C) tabulations will be provided by dose level and overall. For the dose optimization module of the study (Part A1) tabulations will be provided by cohort and overall. For the expansion modules (Parts D, E, F, and G), tabulations will be

provided by tumor type and overall. Some safety analyses may be performed based on the dose escalation, optimization, and expansion modules combined.

Summary tables and listings will be provided for all reported TEAEs, defined as AEs that start on or after the first administration of study treatment up until the SFU visit. A pre-treatment AE which increases in severity on or after the first dose of study treatment will also be counted as a TEAE. The reported AE term will be assigned a standardized preferred term using the current version of the Medical Dictionary for Regulatory Activities (MedDRA).

The causal relationship between the occurrence of an AE and study medication will be judged by the investigator. In the event that a participant experiences repeat episodes of the same AE, then the event with the highest CTCAE severity grade and strongest causal relationship to study medication will be used for purposes of incidence tabulations.

An overview of the number and percentage of participants who experience TEAEs will be presented. This summary will include the number and percentage of participants with any TEAEs, serious TEAEs, related TEAEs (related to UCB6114, TFD/TPI [Part B], any individual component of mFOLFOX6 [Part C], or more than 1 of the treatments [Part B and Part C]), discontinuation due to TEAEs, CTCAE Grade 3 or 4 TEAEs, DLTs, AEs leading to death, and TEAEs leading to death; event counts will also be included against each of these categories.

In addition, the following summaries will be presented by MedDRA System Organ Class, High Level Term and Preferred Term:

- Incidence of all TEAEs, serious TEAEs, and non-serious TEAEs

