- Incidence of TEAEs by maximum relationship and maximum CTCAE severity grade
- Incidence of TEAEs leading to a temporary interruption and/or reduction in study treatment
- Incidence of TEAEs leading to discontinuation of study treatment
- Incidence of fatal TEAEs by relationship
- Incidence of adverse events of special interest (AESIs) (Hy's Law – see Section 9.2.6)
- Incidence of infusion-related (hypersensitivity) reactions

For the dose escalation and optimization modules, the observed DLT rate in each dose cohort will be calculated by the crude proportion of participants who experience DLT. Multiple concurrent AEs leading to DLT will be considered a single DLT.

Deaths that occur on study (defined as during treatment or within 30 days of treatment discontinuation) will be reported in a participant listing, which will include the primary cause of death and the number of days between the date of the final dose of study medication and death.

Observed values and changes from Baseline in clinical chemistry, hematology, urinalysis, and coagulation parameters will be summarized at each visit. In addition, for each of these parameters, the Baseline value, the minimum, maximum, average, and last post-Baseline value for each participant will be summarized by cycle using descriptive statistics. These post-Baseline summary measures will be calculated based on laboratory assessments performed at the scheduled time points common to all cycles of study treatment.

Laboratory values will be assigned severity grades when available using the NCI CTCAE criteria. Directional shifts in laboratory toxicity grades (comparing Baseline grade with worst post-Baseline grade) will be analyzed using standard shift tables, presenting the number and proportion of participants and their maximum grade shift. For analytes without a CTCAE severity grade assigned, the shift table will present directional shifts from Baseline to above or below the laboratory standard normal range using the maximum increase and/or decrease observed throughout the course of treatment/observation.

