**Progression-free survival (PFS)** is defined as the time in days from first dosing date to the date of the first documented objective disease progression or death due to any cause, whichever occurs first. Participants who died without a documented objective disease progression will be considered to have progressed on the date of their death. Participants who did not progress or die will be censored on the date of their last available (scheduled or unscheduled) tumor assessment. Participants who did not have any on-study tumor assessments and did not die will be censored on the date of their first dose of study treatment. Participants who discontinued early without documented objective disease progression or death will be censored on the date of their last available (scheduled or unscheduled) tumor assessment at which a lack of objective disease progression was determined. Participants who started anti-cancer therapy without a prior documented objective disease progression will be censored on the date of their last available (scheduled or unscheduled) tumor assessment prior to the initiation of the subsequent anti-cancer therapy. A sensitivity analysis will be performed taking into account both objective progressive disease and clinical disease progression, as determined by the investigator, in the calculation of PFS.

**Overall Survival (OS)** is defined for all participants in the study as the time in days from the date of first dosing to the date of death from any cause. Participants will be followed up to ascertain their survival status at the SFU Visit (within 30 days after their final dose of study treatment) and at the Final Visit (3 months after their final dose of study treatment); they will not be followed up beyond this time point. For participants who discontinued early from the study or discontinued study treatment due to disease progression and were not known to have died, OS will be censored on the date of last contact.

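### The TEAE window closes at an SFU visit with no fixed day, out of step with the 30-day windows for recording AEs and counting on-study deaths

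*Protocol*

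**What the plan says.** Protocol Section 10.3.1 presents TEAEs, "defined as AEs that start on or after the first administration of study treatment up until the SFU visit", and adds pre-treatment AEs that worsen after the first dose. Tables 3-1 and 3-2 list the primary endpoints of Parts A and A1, and of Parts B and C, as "Incidence of TEAEs Severity of TEAEs Incidence of DLTs".

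The day of the SFU visit is described in more than one way:

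- Table 1-4 (Part A) heads the SFU column "Within 30 days after last dose". Table 1-7 (Part B) has "Within 30 days after final dose", and Table 1-8 (Part C) matches it. Figure 1-3 allows up to 30 days in Part A1.
- Section 10.4.1.1 refers to the "SFU Visit (within 30 days after their final dose of study treatment").
- The synopsis, under treatment groups and duration, puts the visit at approximately 30 days after discontinuation, and only where possible.
- Footnote f of Table 1-4 says: "When participants are unable to attend the SFU or Final Visit, it will not be considered a protocol deviation".

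Three other passages set periods that ought to match the TEAE window:

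- Footnote y of Table 1-4 says "AEs will be recorded up to 30 days after the last dose of study medication". The AE footnotes of Tables 1-5 to 1-8 set the same 30 days for Parts A1, B and C.
- Section 9.2.1 instead collects AEs and SAEs until the follow-up visit.
- Section 10.3.1 lists "Deaths that occur on study (defined as during treatment or within 30 days of treatment discontinuation").

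**The concern.** The end of the window for a primary endpoint is a visit date, and the protocol lets that date fall anywhere in the 30 days after the last dose or, in Part A, not occur at all without this being a deviation. The other safety windows are fixed lengths of time. Two participants with the same AE on the same day after their last dose can therefore be counted differently, solely because of when the SFU visit was booked.

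Take an AE that begins on Day 25 after the last dose in a participant seen for the SFU visit on Day 14. Under the schedule footnotes it is recorded. Under Section 10.3.1 it is not a TEAE, so it is absent from the overall, severity, relationship and seriousness tables. If it is fatal within the 30 days, the participant appears in the on-study death listing but not among fatal TEAEs. Section 10.3.1 tabulates AEs leading to death beside TEAEs leading to death, so a reader of the report would see the discrepancy.

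This is not a detail waiting for the SAP. The protocol states an end date and states it inconsistently with its own 30-day windows. A SAP that used 30 days would depart from the protocol's definition, and Section 9.2.1 would still tell sites to stop collecting at the visit.

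**Working it through.** The protocol gives no figure to reproduce. The check is a comparison of windows, then a simple measure of the gap.

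**The windows side by side**

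- TEAE (Section 10.3.1): starts at the first dose; ends at the SFU visit, on whatever day that falls.
- SFU visit (schedules, Section 10.4.1.1): Day 0 to Day 30 after the last dose, with no lower limit. Synopsis: about Day 30, where possible.
- AE recording (footnotes for Parts A, A1, B and C): to Day 30 after the last dose.
- AE collection (Section 9.2.1): to the follow-up visit.
- On-study death (Section 10.3.1): to 30 days after treatment discontinuation, an anchor worded differently from the last dose.

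The TEAE window and Section 9.2.1 therefore agree with each other, and both disagree with the footnotes and the death window. Only an SFU visit on Day 30 brings them together.

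**Size of the gap.** For an SFU visit on Day d after the last dose, the part of the 30-day recording window outside the TEAE window is (30 - d)/30. The values of d are assumptions, because the documents give no actual visit days:

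- Day 7: 23/30 = 76.7%
- Day 14: 16/30 = 53.3%
- Day 21: 9/30 = 30.0%
- Day 28: 2/30 = 6.7%
- Day 30: 0%

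These are shares of follow-up time. They equal shares of post-dose AEs only if onsets are spread evenly over the 30 days, which is a further assumption.

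**On the participant scale.** Let p be the assumed 30-day incidence of a first post-dose event, with constant hazard. The incidence counted by Day d is 1 - (1 - p)^(d/30).

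- p = 10%: 9.4% counted at Day 28, 4.8% at Day 14
- p = 20%: 18.8% at Day 28, 9.9% at Day 14
- p = 30%: 28.3% at Day 28, 15.3% at Day 14

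This covers only the period after the last dose. Someone who already had a TEAE on treatment stays in the any-TEAE count regardless, so the effect on overall TEAE incidence is smaller than these differences suggest, and it cannot be estimated from the documents.

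**No SFU visit.** The TEAE definition supplies no substitute date, so the window has no stated end. Any AE recorded up to Day 30 would then still count.

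**The case against.** The strongest reply is that the synopsis describes an SFU visit at about 30 days. Read with the schedules, that makes it a visit near the end of the month, and the loss is then close to the Day 28 figure or nil. This stands as a limit on size: the Day 7 and Day 14 values show how the gap grows and are not expected values. It does not remove the gap, because the schedules set no lower limit. Section 9.2.5 also has a pregnant participant return for an SFU visit at which stopping of study medication is instructed, so an early visit is contemplated in at least one case.

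Second, Section 9.2.1 ends collection at the follow-up visit, consistent with the TEAE definition. That is correct. It means collection to Day 30 rests on the schedule footnotes and is itself contradicted, which is one more passage to reconcile.

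Third, the consequences for decisions are limited. Escalation in Parts A, B and C rests on Cycle 1 DLTs, which do not use the SFU cut-off. The SMC considers all available safety data, no formal testing is planned in these parts, and SAEs thought to be drug-related are reportable whatever their timing. All of this stands.

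A reader might also infer more than the text supports:

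- That the window is shortest for participants who deteriorate or move to new therapy. No passage ties SFU timing to the reason for stopping.
- That dose levels cannot be compared. This would need SFU timing to differ by dose, and nothing suggests it does.
- That missed visits cause undercounting. A missed visit leaves the window open.
- That non-attendance is excused in every part. The statement that it is no deviation stands in the Part A footnotes only; elsewhere there is only the synopsis proviso, and Section 7.2 asks sites to facilitate the visit for those who withdraw.

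**Conclusion.** The inconsistency is real and worth correcting. A primary endpoint in Parts A, A1, B and C ends at a visit with no fixed day, while the schedule footnotes and the on-study death definition use 30 days and Section 9.2.1 uses the visit. An AE with onset after an early SFU visit and within 30 days of the last dose is recorded under the footnotes and excluded from all TEAE tables by a stated rule. Without an SFU visit the window has no defined end.

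The size depends on visit days that the documents do not give. It is near zero if visits occur at about Day 30, about 7% of the post-dose window at Day 28, and larger for earlier visits. It concerns only AEs after the last dose and leaves Cycle 1 DLT decisions untouched. The documents establish an ill-fixed window; they do not establish bias in a particular direction between dose levels.

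**What to change.** In Section 10.3.1, define a TEAE as an AE with onset or worsening from the first dose of any study treatment through 30 days after the last dose of any study treatment, irrespective of when or whether the SFU visit takes place. Naming any study treatment matters in Parts B and C, where a participant may stop the chemotherapy and continue UCB6114.

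Give the collection period in Section 9.2.1 and the on-study death window the same anchor (last dose) and the same 30 days. The three windows then coincide, and no AE recorded within those 30 days falls outside the TEAE window. The synopsis and the schedules should also describe the SFU visit in the same terms, although its day would no longer determine the endpoint.

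The cost is small: a few sentences of text, and AE collection to Day 30, for example by phone, when the SFU visit is early or missed. The schedule footnotes already require that collection.
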